Data on PCPs and their patients at Penn Medicine, UW Medicine, and Lancaster General Health will be obtained from Clarity (Epic's data reporting database). Clinician data includes gender and type of medical degree. Patient information includes demographic information, information about comorbid conditions (including diabetes, hypertension, and chronic kidney disease, and comorbid conditions needed to calculate the Charlson Comorbidity Index), contraindications for flu vaccine, appointment data, and flu vaccination administration.

--Randomization—

Primary care clinic level randomization will occur electronically. We will randomize clinics 2:1 to the nudge arm or control arm using covariate-constrained randomization.¹⁰ Covariate-constrained randomization first enumerates a large number (e.g., 50,000) of possible intervention allocations. Then, a measure of covariate balance is computed with respect to a set of pre-specified covariates for each possible allocation. Finally, from a subset of possible allocations that achieve adequate covariate balance, one is randomly chosen as the final allocation of interventions for the study. We will implement a version of covariate-constrained randomization that stratifies by health system (Penn and UW) and balances the distribution of clinic size and panel risk across arms. The randomization procedure will be implemented in R¹¹ using the cvcrand package.¹² For the replication trial at Lancaster General Health, we will implement covariate-constrained randomization using the cvcrand package to balance the distribution of clinic size and panel risk across arms.

Within the high-risk patient subgroups, stratifying by intervention clinics, patients will be randomized 1:1 in Way to Health using permuted block randomization using random block sizes of 2, 4, and 6 to receive the additional intensification bidirectional text messaging nudge or standard messaging.

9. Analysis plan

Prior to analyses, we will produce data summaries to assess data quality, data distribution, and randomization success. To ensure even comparison across practices and arms, we will classify eligible patients at 4 days before a scheduled appointment for a new or return visit with their primary care clinician as being enrolled in the study. The primary analysis will be performed using an intention-to-treat approach. Specifically, patients who

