do not show up to the first scheduled clinician visit will be considered enrolled and included in the primary analysis.

--Power Calculations--

For the following power calculations, we used an adjusted Type I error of 0.025 to account for two comparisons: 1) clinic-level nudges versus usual care, and 2) intensification for high-risk patients versus no intensification within practices where clinic-level nudges are provided. Based on retrospective data from our health systems, we will have 85% power to detect a 7-percentage point difference in the flu vaccine completion rate for comparison #1. This calculation assumed N=48 participating clinics across the two sites, an average cluster size of n=1385 patients, and an intracluster correlation (ICC) of 0.02. For comparison #2, we will have at least 99% power to detect a 2-percentage point difference even if the rate of vaccination in the high-risk group is 50%, the most conservative rate with respect to power. This calculation assumed 1:1 individual-level randomization of n=1000 high-risk patients within each of N=32 clinics that will be randomized to receive clinic-level nudges. These power calculations used combined retrospective data from Penn and UW to estimate the average number of patients per clinic and the number of high-risk patients who will be randomized. We expect to have greater power for both comparisons at the replication site which comprises more clinics and patients.

--Statistical Analysis--

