We will test each of the four linear contrasts of the parameters estimated from the GEE model. We will use a Bonferroni correction for the first two contrasts, aligning with how the study was powered (i.e., two-sided significance level of 0.025 for the first two contrasts). We will consider contrasts 3 and 4 as exploratory, and thus we will not correct the corresponding p-values for multiple testing. Results will be reported on the odds ratio scale, including 95% confidence intervals. Confidence intervals for contrasts 1 and 2 will incorporate the Bonferroni correction used for the two tests.

Sensitivity Analyses to Evaluate Model Specifications

As a sensitivity analysis, we will restrict the data to high-risk patients at active clinics and estimate the main effect of intensive vs standard text messaging, specifying an exchangeable working

correlation within clinics. As another sensitivity analysis, we will use an exchangeable working correlation at the clinic level after duplicating each clinic's data, assigning one 1 and one -1 for patients without an individual-level assignment, and removing the record for each high-risk patient an intervention clinic corresponding to the opposite of the individual-level randomized assignment that was received. Duplicated clinics will be treated as independent while observations within clinic will be treated as exchangeable. In this way, duplicated records will be treated as independent. Using this approach, we will re-test the main effect of A_1 , i.e., $2\beta_1$, to evaluate sensitivity to specification of the working correlation. We will use a t-distribution with degrees of freedom equal to the number of clinics (47) minus the number of mean model parameters to construct a confidence interval for $2\beta_1$. If the interval does not include 0 (log odds ratio scale) we will reject the null and conclude there is a significant effect of clinic nudges compared to usual care.

Sensitivity Analyses to Evaluate Protocol Deviations

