Patients observed in the first six weeks at Penn did not receive the full intervention due to a switch from using API (Application Programming Interface) to RPA (Robotic Process Automation). Specifically, patients at intervention clinics at Penn did not receive pended orders. In our primary analyses, we will include these patients as having received pended orders, following the intent-to-treat principle. In sensitivity analyses, we will repeat our analyses of primary and secondary outcomes after excluding this group who did not receive the full intervention. To mitigate any confounding effects of time (i.e., patients more likely to complete vaccinations earlier in the season) we will also exclude all Penn control arm patients during the first six weeks of the trial. Since this issue was not encountered at UW, all UW patients during this six week time period will be included in this per-protocol analysis.

Next, we will leverage this subset of intervention clinic patients who did not receive pended orders to estimate the effect of texting alone (standard texting versus control and intensive texting versus control) on completion at the day of eligible visit. We will also leverage this subset of patients to estimate the effect of ordering amongst low-risk patients who received text messaging as well as amongst high-risk

subjects who received either standard or intensive text messaging. There was a different subset of patients in intervention clinics who did not receive text messaging. We will utilize this group to estimate the effect of ordering alone versus control. These analyses will be exploratory, and their feasibility will depend on the number of patients in each group who did not receive the full planned intervention components. Analyses will mimic the approach specified for the primary and secondary outcomes (e.g., GEE, weighting and replicating when appropriate).

Analytical Plan for Exploratory Analyses

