To examine the effect of the intervention on flu vaccination ordering, a GEE with a binary outcome indicating whether the pended order was signed or cancelled will be fit. The rates of flu vaccination completion will be compared between (1) usual care, (2) clinic level nudge only, and (3) clinic-level nudges with high-risk intensification using the same weighted and replicated approach described for the primary outcome and the mean model given in equation (1). We will again use an independence working correlation for these comparisons and perform sensitivity analyses to assess sensitivity to specification of the working correlation.

Exploratory subgroup analyses will examine the effect of the clinic-level nudge versus usual care among patients who are 1) identified as low-risk for completion and 2) identified as high-risk for completion, and 3) seen at Penn versus UW. For (1), we will restrict the data set to low-risk patients in the active and control clinics. Then, we will fit a GEE model with an indicator for clinic randomized assignment and variables used in the covariate constrained randomization. We will fit the model with a logit link and exchangeable working correlation. For (2), we will subset the data to patients deemed high-risk in both active and control arms, we will fit a GEE model with an indicator for clinic randomized assignment, indicator for individual-level randomized assignment, interaction between the clinic- and individual-level randomized assignments, and variables used in the covariate constrained randomization. We will use the weighted and replicated approach described previously, replicating each high-risk patient in the control arm and assigning them each a weight of 1 while assigning each high-risk patient in the

intervention clinics a weight of 2. We will fit the model with a logit link and independent working correlation. We will test the main effect of the clinic-level nudge and the main effect of standard versus intensive texting. We will test contrasts 1), 3), and 4). For investigating possible effect heterogeneity by health system, we will re-fit models for our primary and secondary outcomes separately on data from Penn and UW.

To investigate potential effect heterogeneity over time, we will fit GEE models for our primary and secondary outcomes with the addition of month and month-by-treatment interactions. The model will take the following form:

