$$\text{logit} (\Pr(Y = 1 | A_1, A_2, T, X)) = \beta_0 + \beta_1 A_1 + \beta_2 A_1 A_2 + \beta_3 T + \beta_4 A_1 T + \beta_5 A_1 A_2 T + \beta_6^T X, \quad (2)$$

where T is a categorical variable indicating study month. We will use the weighted and replicated approach and an independent working correlation structure. We will first assess whether the effect of text messaging style differs over time. If we do not find evidence of effect heterogeneity for text messaging style, we will drop A_2 from the model and focus only on the effect of pended orders over time using the following model:

$$\text{logit} (\Pr(Y = 1 | A_1, A_2, T, X)) = \beta_0 + \beta_1 A_1 + \beta_2 T + \beta_4 A_1 T + \beta_5^T X, \quad (3)$$

Inference will focus on the interaction effect, β_4 , and we will not use any weighting or replicating to fit this model. We will fit this model using an independent working correlation.

Lastly, we will determine which high-risk intensification subgroups experienced the greatest benefits of the clinic- and individual-level nudges. Using the data set restricted to high-risk individuals, we will fit the following model:

$$\text{logit} (\Pr(Y = 1 | A_1, A_2, Z, X)) = \beta_0 + \beta_1 A_1 + \beta_2 A_1 A_2 + \beta_3 Z + \beta_4 A_1 Z + \beta_5 A_1 A_2 Z + \beta_6^T X, \quad (4)$$

where Z is a single, high-risk criteria. We will fit model (2) separately for each high-risk criteria which will allow us to determine which high-risk intensification subgroups experienced the greatest benefits of the clinic- and individual-level nudges. We will again use the weighted and replicated approach,

duplicating each control arm patient and assigning them a weight of 1 while assigning each intervention clinic patient a weight of 2. We will use an independent working correlation structure.

We now provide details about the interaction effects of interest. First, note that the main effect of A_1 amongst $Z = 1$ is:

$$\begin{aligned}\beta_0 + \beta_1 + \beta_2 A_2 + \beta_3 + \beta_4 + \beta_5 A_2 + \beta_6^T X - (\beta_0 - \beta_1 - \beta_2 A_2 + \beta_3 - \beta_4 - \beta_5 A_2 + \beta_6^T X) \\ = 2\beta_1 + 2\beta_4\end{aligned}$$

Similarly, the main effect of A_1 amongst $Z = 0$ is:

$$\begin{aligned}\beta_0 + \beta_1 + \beta_2 A_2 + \beta_6^T X - (\beta_0 - \beta_1 - \beta_2 A_2 + \beta_6^T X) \\ = 2\beta_1\end{aligned}$$

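### The exploratory month and site models set no rule for Penn's first six weeks without pended orders, so an apparent change in effect over time may partly reflect order availability

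*SAP*

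**What the plan says.** Under Sensitivity Analyses to Evaluate Protocol Deviations, the SAP states that in the first six weeks "patients at intervention clinics at Penn did not receive pended orders", because of a software switch, and that UW did not have this problem. The primary analyses keep these patients as assigned. A sensitivity repeat of the primary and secondary outcome analyses removes them, together with Penn control patients from the same weeks, and keeps all UW patients.

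The next section, Analytical Plan for Exploratory Analyses, specifies two heterogeneity analyses. For site, "we will re-fit models for our primary and secondary outcomes separately on data from Penn and UW". For time, models (2) and (3) add study month and month-by-treatment terms to data pooled over both systems. If texting style shows no heterogeneity over time, A2 is dropped so as to "focus only on the effect of pended orders over time", with inference on the A1-by-month term. That section states no exclusion of the six weeks, no term for order availability, no system-by-month term and no caution on interpretation.

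**The concern.** The missing component was confined to one system and to the start of the season. It therefore coincides with both factors under study, month and site. In model (3) the A1-by-month term would combine any real seasonal change with whether orders existed at Penn at all. Intention to treat justifies reading A1 as the effect of assignment. It does not justify reading it as the effect of pended orders in weeks when most intervention patients may have had none. The label is loose in any case, because protocol section 8.2 also gives intervention clinics patient texts and peer-comparison feedback.

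At stake is an exploratory message that the intervention gains strength after the opening weeks, or works less well at Penn, when the cause was delivery. The texting contrast is less exposed: it compares patients randomized within the same clinics, and both of its arms lacked orders alike.

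**Working it through.** **The plan's own figure.** The documents give no figure for the heterogeneity analyses. The nearest is the protocol's power statement (section 9), "85% power to detect a 7-percentage point difference in the flu vaccine completion rate for comparison #1", with "N=48 participating clinics across the two sites, an average cluster size of n=1385 patients, and an intracluster correlation (ICC) of 0.02". It supplies a 7-point effect as a scale. Inputs: "We will randomize clinics 2:1 to the nudge arm or control arm" (section 8.2), so 32 and 16 clinics, and a "two-sided significance level of 0.025 for the first two contrasts" (SAP).

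- Design effect = 1 + (1385 − 1) × 0.02 = 28.68.
- Effective sizes: 16 × 1385 / 28.68 = 773 control and 32 × 1385 / 28.68 = 1,545 intervention.
- The control rate is not given. Two-proportion power for a 7-point difference is 86.8% at a control rate of 30%, 84.6% at 35%, 83.2% at 40%, 82.6% at 45%, 82.9% at 50%, 83.9% at 55% and 85.8% at 60%. The stated 85% is broadly reproduced.

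**Size of the distortion.** Penn's share of planned enrolment (protocol 5.6 and 5.7) is 51,152 / (51,152 + 28,705) = 51,152 / 79,857 = 0.641. Assumptions that are not in the documents:

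- the full intervention has the same true effect in every month and at both systems;
- a share s of that effect comes from the pended order;
- the start is 1 September, so six weeks (42 days) cover all 30 days of month 1 and 12 of 31 days of month 2;
- both systems accrue in proportion to planned enrolment, evenly over 26 weeks.

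Apparent effect as a fraction of the true effect:

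- month 1, pooled: 1 − 0.641 × s
- month 2, pooled: 1 − 0.641 × s × 12/31
- months 3 to 6: 1
- Penn overall, with UW = 1: 1 − (6/26) × s

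| s | Month 1 | Month 2 | Penn relative to UW | Month 1 if the true effect is 7 points |
|---|---|---|---|---|
| 0.25 | 0.84 | 0.94 | 0.94 | 5.9 |
| 0.50 | 0.68 | 0.88 | 0.88 | 4.8 |
| 0.75 | 0.52 | 0.81 | 0.83 | 3.6 |
| 1.00 | 0.36 | 0.75 | 0.77 | 2.5 |

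The SAP reports odds ratios, so the scale needs checking. At an assumed control rate of 40%, 7 points is an odds ratio of 1.330, and the month 1 value at s = 0.5 is 1.215. On the log scale, ln 1.215 / ln 1.330 = 0.195 / 0.285 = 0.68, the same ratio.

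Accrual matters for the site figure. If 40% of Penn's patients fell in the six weeks (a front-loaded season), Penn relative to UW would be 1 − 0.40 × s, or 0.90 to 0.60.

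**Would the tests pick it up?** Model (3) was simulated with a constant true effect (independence working correlation, clinic-clustered robust errors, 5-df Wald test at 0.05, 500 runs per setting, an assumed 30 Penn and 18 UW clinics).

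| Comparison | Setting | Rejection rate |
|---|---|---|
| Month by treatment | no missing component | 11–16% |
| Month by treatment | s = 0.5 | 30–48% |
| Month by treatment | s = 1 | 73–93% |
| Month by treatment | both Penn arms excluded for six weeks | 13–17% |
| Penn versus UW | no missing component | 7–9% |
| Penn versus UW | orders missing | 6–13% |

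The month baseline exceeds 5% because the robust Wald test is uncorrected. With orders missing, the simulated Penn/UW odds-ratio ratio was about 0.89 to 0.98. After the exclusion, the month and site ratios returned to about 1.00.

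**The case against.** The strongest reply is that the rule already exists. The sensitivity repeat covers the analyses of primary and secondary outcomes, and the month and site models are fitted to those same outcomes. That inclusion of the six weeks is not stated outright is true. But the repeat sits under an earlier, separate heading and names neither the month models nor the site re-fits, so stretching it to them is strained. If the sponsor intended it, one sentence would settle the matter.

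Several other points stand. The distortion is zero if pended orders have no effect, and its size depends on s, the start date and accrual, none of which is given. At s = 0.5, most simulated runs showed no significant month artefact. Three-month completion could be diluted differently. The SAP discloses the failure and plans to use the same patients to estimate texting alone, so readers will have part of the explanation.

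A reader might infer three stronger claims that the documents do not support:

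- That the plan will report a false site difference. It plans separate re-fits without a formal Penn-versus-UW test, and the simulated site test rarely rejected.
- That Objective 3 is compromised. It names clinician, patient and practice characteristics, not calendar time.
- That UW's first six weeks should be dropped from the pooled month terms, or a formal interaction test added. UW's early data are valid, and neither step is needed to repair this gap.

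**Conclusion.** The concern holds in a limited form. As written, the month-by-treatment models confound order availability at Penn with study month, and the Penn re-fit is diluted relative to UW. The month distortion is the more serious one and can be large if orders carry half or more of the effect. The site shift is modest. Both results require that pended orders have some effect, and both rest on the accrual and start-date assumptions listed above. The analyses are exploratory and uncorrected for multiplicity by design. The primary conclusion is not affected, because it estimates the effect of assignment.

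**What to change.** In the Analytical Plan for Exploratory Analyses:

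1. Fit models (2) and (3) and the Penn re-fit also with both Penn arms excluded for the first six weeks, and base any conclusion about time or site on those fits.
2. Show month effects by health system, because the first month would then contain UW patients only and month would otherwise be entangled with site. Note that week 7 falls inside study month 2, so Penn's first retained month is partial.
3. Compare Penn with UW over the same weeks, from week 7 onward.
4. Keep the all-data fits, labelled as effects of assignment under the implementation delivered.
5. Describe A1 in model (3) as assignment to the clinic-level intervention, not as the effect of pended orders.

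The cost is SAP wording and a few extra fits on existing data. Early-season estimates would rest on UW alone and be less precise. The by-system fits would also have fewer clinics to support robust standard errors, from a total that the documents give as 48 (protocol) and as 45 and 47 (SAP).
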